#### 4.3.3.2. Main Analytical Approach

See Appendix 6.3.2 for MIBS-4 scoring information. Only data from those participants who meet criteria for the Full Analysis set will be analyzed. Data for this secondary endpoint will be analyzed via a repeated measures ANOVA comparing changes in participant's Migraine Interictal Burden Scale (MIBS-4) scores from baseline (Visit 2) to each of the 4-week treatment periods (Visit 3, 4, and 5). Significant changes will be followed up using within groups, repeated measures *t*-tests as needed.

#### 4.3.4. Change in Migraine Days from Baseline to Each 4-Week Treatment Period

##### 4.3.4.1. Definition of Endpoint

Headache and Migraine data will be recorded by the participants into an electronic daily headache diary (DHD) throughout the study. The DHDs are web-based and can be completed on any internet enabled device using the participant's unique log in credentials. Site personnel will be responsible for instructing participants on the requirement for timely and daily completion of the DHD.

Clinic visits are to occur every 28 days throughout the study; however, in practice, there may or may not be an exact 28-day duration between two consecutive visits. As such, participants may have more or less than 28 diary entries between two consecutive visits. To account for this, the following will be utilized:

- **Baseline:** eDiary information entered during the *last* 28 continuous days of the run-in period will serve as the “baseline” for calculating change from baseline. For example, if a participant's run-in period is 31 days long, and the participant entered eDiary information for all 31 days, the last 28 days (leading up to first drug administration) will be used to calculate and derive endpoint variables, with the first three eDiary entries (days 1, 2, and 3) being discarded from the analysis datasets.
- **Treatment Months:** If a participant enters more than 28 days of eDiary information between clinic visits during the treatment phase of the study, the *first* 28 continuous day's eDiary entries for each period/month will be used for analyses. For example, if a participant has a duration of 31 days between Visit 2 and Visit 3, and the participant entered eDiary information for all 31 days, the first 28 days (following Visit 2) of eDiary information will be used to calculate and derive endpoint variables, with the last three eDiary entries (days 29, 30, and 31) being discarded from the analysis datasets.

Migraine headache days are defined in this study as an attack within a calendar day (00:00 to 23:59) that meet at least one of the two following criteria:

1. A headache attack that includes all of the following criteria:

This document, including any source code, is the property of [Clinvest Research LLC](#), and may contain proprietary, confidential, or legally privileged information. No part of this report, or any information contained therein, may be disseminated without the written consent of [Clinvest Research LLC](#).

A. Headache attacks lasting 4-72 hours (untreated or unsuccessfully treated)

B. Headache has at least two of the following four characteristics:

1. unilateral location
2. pulsating quality
3. moderate or severe pain intensity
4. aggravation by or causing avoidance of routine physical activity (e.g., walking or climbing stairs)

C. During headache at least one of the following:

1. nausea and/or vomiting
2. photophobia and phonophobia

2. A headache attack of any duration with relief (defined as a “Yes” answer to the eDiary question “*Did you get relief from taking the above medication(s) yesterday?*” [HD\_RLFYN]) from the following migraine-specific acute medication(s):

- Advil (Ibuprofen)
- Aleve (Naproxen)
- Amerge (Naratriptan)
- Axert (Almotriptan)
- Butabitol
- Cafergot (Ergotamine Tartrate/Caffeine)
- Cambia (Diclofenac Potassium)
- Cefaly
- DHE 45 (Dihydroergotamine)
- Ergomar (Ergotamine Tartrate Sublingual Tablets)
- Excedrin Migraine
- Fioricet
- Fiorinal
- Frova (Frovatriptan)
- gammaCore Sapphire
- Imitrex (Sumatriptan)
- Indocin (Indomethacin)
- Maxalt (Rizatriptan)
- Midrin (Isometheptene Mucate, Dichloralphenazone and Acetaminophen)
- Migerot (Ergotamine Tartrate/Caffeine Suppository)
- Migranol
- Migril (Ergotamine, Cylizine, and Caffeine)
- Namenda (memantine)
- Onzetta (Sumatriptan Nasal Powder)
- Prednisone

This document, including any source code, is the property of [Clinvest Research LLC](#), and may contain proprietary, confidential, or legally privileged information. No part of this report, or any information contained therein, may be disseminated without the written consent of [Clinvest Research LLC](#).

- Relpax (Electriptan)
- Reyvow (Lasmiditan)
- Sumavel (Sumatriptan Needleless Injection)
- Tivorbex (Indomethacin)
- Treximet (Sumatriptan/Naproxen)
- Tylenol (Acetaminophen)
- Zembrace (Sumatriptan injection)
- Zomig (Zolmitriptan)
- Zorvolex (Diclofenac)

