Visit 2 will take place 28 to 33 days following Visit 1. Those participants who (1) continue to meet eligibility criteria (2) experienced 4-20 migraine days that meet ICHD-III criteria for migraine and (3) have completed at least 23/28 diary days will be eligible to be enrolled into the study. At this visit a physical examination (including vital signs) will be performed, WOCB will complete a urine pregnancy test, and all participants will complete the PHQ-9. Medical history and/or adverse events and concomitant medications will be reviewed and updated as needed. Participant's DHD will be reviewed for compliance, and participants will complete the following questionnaires:

- MFIQ
- MIBS-4
- WPAI-M
- SDSF
- GSE-SF
- BMWS
- FAMS

Finally, all eligible participants will receive an injection of 140 mg erenumab-aooe. Participants will continue completing diary headache diaries for the remainder of the trial.

Visits 3-5 will take place on days 29 (+/-3d), 57 (+/-3d), and 85 (+/-3d), following Visit 2. At each visit: a physical examination (including vital signs) will be performed, WOCB will complete a urine pregnancy test, and all participants will complete the PHQ-9. Medical history

This document, including any source code, is the property of [Clinvest Research LLC](#), and may contain proprietary, confidential, or legally privileged information. No part of this report, or any information contained therein, may be disseminated without the written consent of [Clinvest Research LLC](#).

and/or adverse events and concomitant medications will be reviewed and updated as needed. Participant's DHD will be reviewed for compliance, and participants will complete the following questionnaires:

- MFIQ
- MIBS-4
- WPAI-M
- SDSF
- GSE-SF
- BMWS
- FAMS

Finally, all eligible participants will receive an injection of 140 mg erenumab-aooe. Visit 5 (End of Study) will not include injections but will include comprehensive metabolic panel (CMP) laboratory.

This document, including any source code, is the property of [Clinvest Research LLC](#), and may contain proprietary, confidential, or legally privileged information. No part of this report, or any information contained therein, may be disseminated without the written consent of [Clinvest Research LLC](#).

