#### 4.1.1. Missing Data

Missing data for full analysis population participants will be imputed as follows:

- Missing values on questionnaire items will be handled according to the questionnaire's scoring manual. When no guidance is specified in a questionnaire scoring manual, missing items will be left null and the score and/or sub-score will be imputed using a last observation carried forward (LOCF) method. This type of imputation replaces the missing value with the last observation value obtained for the participant.
- Missing DHD entries (Monthly Migraine Days) will be imputed as follows:
  - < 14 DHDs completed: Participant's average MMDs for that study period will be replaced with their last study period's MMD using the LOCF method.
  - $\geq 14$  DHDs completed: Participant's average MMDs for that study period will be imputed based on the data available in that study period and prorated to 28 days.
- Missing Garmin data (Steps and Sleep) will be imputed as follows:
  - < 14 days synced: Participant's average steps and/or sleep for that study period will be replaced with their last study period's steps and/or sleep using the LOCF method.
  - $\geq 14$  days synced: Participant's steps and/or sleep for the missing day will be imputed using the participant's mean steps and/or sleep for the data available in that study period.

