#### **4.3.4.2. Main Analytical Approach**

Only data from those participants who meet criteria for the Full Analysis set will be analyzed. Participants will be asked to record diary data each day for the previous day (24-hour period). If a participant does not experience a headache in the previous 24-hour period, the diary must still be completed as instructed. Participant's diaries may vary day to day based on their responses. All participants should have at least 80% compliance with diary completion throughout the length of the study. Participants will record headache severity, symptoms, use of acute medications, as well as additional assessments as required.

This frequency of migraine days will be derived from the participants' eDiary entries. The eDiary entries are based on the count of days with migraine headaches for each 28-day time points (baseline, treatment month 1, treatment month 2, treatment month 3). Participants with less than 80% diary compliance for any study period (defined as <23 completed eDiaries during that study period/month) will be considered Missing Data for that entire study period/month. The number of migraine days for these study periods/months will be imputed using the LOCF method. Data for this secondary endpoint will be analyzed via a repeated measures ANOVA comparing participant's mean change in the number of migraine days from baseline to each of the 4-week treatment periods. Significant changes will be followed up using within groups, repeated measures *t*-tests as needed.

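### The SAP has no clear rule for a treatment month shorter than 28 days: section 4.3.4 undercounts its migraine days, section 4.1.1 would correct this, and neither is given precedence

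*SAP*

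**What the plan says.** SAP 1.2 sets the calendar. For the run-in, "Visit 2 will take place 28 to 33 days following Visit 1". For treatment, "Visits 3-5 will take place on days 29 (+/-3d), 57 (+/-3d), and 85 (+/-3d), following Visit 2".

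SAP 4.3.4.1 builds the diary periods from those visits and notes that "As such, participants may have more or less than 28 diary entries between two consecutive visits". Baseline is the last 28 days of the run-in. The treatment-month rule opens with the condition "If a participant enters more than 28 days of eDiary information between clinic visits during the treatment phase of the study" and then keeps the first 28. There is no matching rule for a shorter month.

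SAP 4.3.4.2 describes the quantity analysed: "The eDiary entries are based on the count of days with migraine headaches for each 28-day time points". It sets the 80% compliance limit as "defined as <23 completed eDiaries during that study period/month) will be considered Missing Data for that entire study period/month", and fills such months by LOCF.

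SAP 4.1.1 has a different diary rule. LOCF applies at "< 14 DHDs completed". With 14 or more, the month's value is based on the available data and prorated to 28 days. This rule is introduced as the handling of missing diary entries. The Version History lists 4.1.1 as the only section revised in version 2.

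**The concern.** Long months are cut to 28 days, short months are not brought up to 28, and baseline is never short. If short months stay as raw counts, every departure from 28 days lowers the on-treatment count relative to baseline. The study has one arm, so there is no control group in which this would cancel. Change in migraine days from baseline to each month is a secondary endpoint, and some of any reported fall could come from visit timing alone.

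The fixed limit of 23 diaries has a related weakness: it does not move with the length of the month. A participant who completes every diary in a very short month could lose that month and have the previous month's value put in its place.

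**Working it through.** **Inputs.** Visit 2 is Day 1. Visit 3 falls on Days 26-32, Visit 4 on Days 54-60 and Visit 5 on Days 82-88 (SAP 1.2 and 1.2.1). The run-in is 28-33 days (SAP 1.2). Entry requires 4 to 20 migraine days per month (SAP 1.2). Two assumptions are not in the documents: a constant daily migraine rate, and the spread of visit dates within their windows.

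**The plan's own cutoff.** 0.80 × 28 = 22.4, which rounds up to 23. The figure reproduces, but only for a 28-day month.

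**Month lengths.**
- Month 1: 26 - 1 = 25 to 32 - 1 = 31 days.
- Month 2: 54 - 32 = 22 to 60 - 26 = 34 days. Month 3 is the same: 82 - 60 = 22 to 88 - 54 = 34.
- Baseline: the run-in is never under 28 days, so its window is always 28 days.

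**Undercount in a fully completed month of L days, without proration.** The share lost is (28 - L)/28.

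| L | Share lost | Days lost at 4 per 28 | Days lost at 20 per 28 | 80% of L, rounded up |
|---|---|---|---|---|
| 22 | 21.4% | 0.86 | 4.29 | 18 |
| 23 | 17.9% | 0.71 | 3.57 | 19 |
| 24 | 14.3% | 0.57 | 2.86 | 20 |
| 25 | 10.7% | 0.43 | 2.14 | 20 |
| 26 | 7.1% | 0.29 | 1.43 | 21 |
| 27 | 3.6% | 0.14 | 0.71 | 22 |
| 28 | 0% | 0 | 0 | 23 |

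Under 4.3.4.2 the 22-day row is not counted at all: 22 completed diaries is below 23, so the month is set to missing and filled by LOCF. That needs one visit at +3 days and the next at -3, so it can occur only in month 2 or 3.

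**Average over participants, after long months are trimmed to 28.**
- Visits on time: zero.
- Visit days uniform within ±1 day. Months 2-3: (2 × 1 + 1 × 2)/9 = 4/9 day, and 0.444/28 = 1.6%. At 4 and 20 migraine days this is 0.06 and 0.32 days. No month lasts 22 days.
- Visit days uniform within ±3 days. Month 1: (1 + 2 + 3)/7 = 0.86 day, and 0.857/28 = 3.1%. Months 2-3: (1×6 + 2×5 + 3×4 + 4×3 + 5×2 + 6×1)/49 = 56/49 = 1.14 days, and 1.143/28 = 4.1%. At 4, 10 and 20 migraine days this is 0.16, 0.41 and 0.82 days. Months under 28 days: 3/7 = 21/49 = 42.9%. Months of exactly 22 days: 1/49 = 2.0% in each of months 2 and 3.

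The 4.1% treats the 22-day month as an undercount. Leaving it out, because 4.3.4.2 would replace it, gives (56 - 6)/48 = 1.04 days, or 3.7%.

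**The same months under 4.1.1.** A complete 22-day month has at least 14 diaries, so its count is multiplied by 28/22 and the month is kept. At a constant rate the undercount is zero for every L.

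**What the period rule does with complete data.** Take Visit 3 on Day 26 and Visit 4 on Day 57, with every diary completed. Month 1 is counted over 25 days. Month 2 lasts 57 - 26 = 31 days, so its last three diaries are dropped. Days 1-56 would have supplied two full 28-day months.

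**The case against.** The strongest reply is that SAP 4.1.1 already solves this. It is the only section changed in version 2, the stated reason was to clarify missing-data handling, and it prorates to 28 days. Section 4.3.4.2 also speaks of 28-day time points, which suggests that a 28-day value was intended. On that reading nothing is undercounted and no complete month is lost.

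Much of this stands. A reader might infer that the SAP certainly builds a fall in migraine days into the endpoint, or that compliant months will often be thrown away. The documents support neither. Both consequences depend on 4.3.4 governing, or on 4.1.1 being read as covering only skipped entries. A complete month is lost only at exactly 22 days. A reader might also cite a 25-day month with 20-22 diaries, which is 80-88% compliance but fails the limit of 23. That month does have skipped entries, so 4.1.1 covers it on its plain wording; it illustrates the conflict between the two cutoffs, not an effect of month length.

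The reply does not close the matter. In a short month with every diary completed, no entry is missing, and 4.1.1 does not say that it applies. The endpoint's own section still has the count and the 23-diary LOCF rule, which contradicts 4.1.1 for 14-22 diaries. The SAP states no order of precedence between its sections.

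**Conclusion.** The point holds as a gap and a conflict in the SAP, with a consequence that is conditional on how they are resolved. Section 4.3.4.1 recognises short months and gives no rule for them. Followed as written, 4.3.4.2 undercounts a short, complete month by (28 - L)/28 in the direction of improvement and discards a complete 22-day month. Section 4.1.1 would remove both effects but does not clearly apply. Two programmers could reasonably produce different migraine-day results from the same data.

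Without proration and at a constant daily rate, the average effect runs from zero with on-time visits to about 3.1% in month 1 and 4.1% in months 2-3 with visits uniform across ±3 days. The upper end is a scheduling assumption, not a forecast, since SAP 4.3.4.1 intends visits every 28 days. For one participant with a 23-day month the loss is 17.9%, or 0.71 to 3.57 days at 4 to 20 migraine days.

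The affected endpoint is secondary. The primary endpoint uses MFIQ item 16 at Visits 2 and 5, not the diary, so it and N = 54 are unaffected.

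**What to change.** 1. Reconcile SAP 4.1.1 and 4.3.4.2 into one diary rule, with one cutoff and one imputation method, and state it in both places or cross-refer.
2. State in 4.3.4.1 that every treatment month with fewer than 28 diary days, including a short month in which every diary was completed, is scaled to 28 days. Alternatively, use fixed analysis windows from the first injection (Days 1-28, 29-56 and 57-84) whatever the visit dates. If Visit 5 falls on Days 82-84 and cuts month 3 short, multiply that count by 28 over the days observed.
3. Define compliance as completed diaries divided by the days available in the period, in place of a fixed number.

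The cost is SAP wording and a small programming change. No new data are needed, and the visit schedule is untouched. With fixed windows, month boundaries may differ from the actual visit dates by up to 3 days.

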4.1. Overall Design

This is a multicenter, open label study assessing the interictal impact of erenumab-aooe in participants with migraine. The study population will consist of 54 participants 18 to 65 years old, with at least 4 and up to 20 migraine days per month (inclusive) following ICHD-III criteria for migraine with or without aura.

At Visit 1, the participant will sign the informed consent indicating they are willing to participate in the study and will provide basic demographic information, have a comprehensive review of their medical history and prior and concomitant medications. A physical and neurological examination (including vital signs) will be performed as well as a 12-lead Electrocardiography (ECG), screening CMP labs, and the PHQ-9 will be completed. Women of childbearing potential (WOCB) will complete a urine pregnancy test. All participants will complete the MFIQ questionnaire. Inclusion and Exclusion criteria will also be reviewed. Participants who meet the study criteria will be dispensed the activity tracker and its associated phone application instructions, as well as their unique Daily Headache Diary (DHD) URL and its instructions. Participants will then enter into a 28-day run-in period. During the 28-day run-in period, all participants will be monitored through the use of electronic Daily Headache Diary (DHD) to ensure they continue to meet all inclusion criteria, and none of the exclusion criteria. During this run-in period, participants will continue treating their migraines and other defined conditions with their usual treatment providing it has been stable for a minimum of 3 months. Daily electronic diaries will be used to assess symptoms and treatment response throughout the run-in period.

Visit 2 will take place 28 to 33 days following Visit 1. Those participants who (1) continue to meet eligibility criteria (2) experienced 4-20 migraine days that meet ICHD-III criteria for migraine and (3) have completed at least 23/28 diary days will be eligible to be enrolled into the study. At this visit a physical examination (including vital signs) will be performed, WOCB will complete a urine pregnancy test, and all participants will complete the PHQ-9. Medical history and/or adverse events and concomitant medications will be reviewed and updated as needed. Participant's DHD will be reviewed for compliance, and participants will complete the following questionnaires:

- MFIQ
- MIBS-4
- WPAI-M

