5.1. Inclusion Criteria

Participants are eligible to be included in the study only if all of the following criteria apply:

1. willing to participate and sign informed consent;
2. ability to understand informed consent and study procedures, including able to use the electronic Daily Headache Diary;
3. in good general health based on investigator's judgment;
4. must be between 18 to 65 years of age, inclusive, at time of Visit 2;
5. have migraine with or without aura meeting the diagnostic criteria listed in the International Classification of Headache Disorders 3rd edition (ICHD-III; Appendix 5);
6. verification of headache frequency through prospectively collected baseline information during the 28-day screening/baseline phase reporting 4-20 migraine days and no more than 20 total headache days;
7. onset of migraine before age 50;
8. able to differentiate migraine from other primary headache types allowed in the study (e.g., tension-type headache);
9. stable history of migraine at least 3 months prior to screening with headache free periods;
10. not currently taking a migraine preventive OR has been taking a stable dose of a preventive for at least 90 days prior to screening and agrees to not start, stop, or change medication and/or dosage during the study period;
* * participants on migraine preventive should have stable headache pattern
11. Must answer "Moderately", "Very Much", or "Extremely" to Item 16 (*In the past 7 days, overall, how much did a migraine affect your usual activities?*) on the Migraine Functional Impact Questionnaire (MFIQ) at screening;
12. women may be included only if they have a negative pregnancy test at screening and baseline, are sterile, or postmenopausal. Women of childbearing potential (WOCBP) whose male partners are potentially fertile (i.e., no vasectomy) must use highly effective birth control methods for the duration of the study (i.e., starting at screening). Definitions of WOCBP, sterile and postmenopausal women, male contraception, and highly effective

and acceptable birth control methods are to be determined based on investigator's judgment;

13. demonstrated compliance with the electronic Daily Headache Diary during the 28-day screening/baseline phase as defined by entry of headache data on a minimum of 23 days;
14. is willing to wear activity/sleep tracker throughout the duration of the trial;
15. has a smartphone and willing to install activity tracker app on phone.

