1.2 Migraine with aura

Description: Recurrent attacks, lasting minutes, of unilateral fully reversible visual, sensory or other central nervous system symptoms that usually develop gradually and are usually followed by headache and associated migraine symptoms.

Diagnostic criteria:

- A. At least two attacks fulfilling criteria B and C
- B. One or more of the following fully reversible aura symptoms:
 - 1. visual
 - 2. sensory
 - 3. speech and/or language
 - 4. motor
 - 5. brainstem
 - 6. retinal
- C. At least three of the following six characteristics:
 - 1. at least one aura symptom spreads gradually over ≥ 5 minutes
 - 2. two or more aura symptoms occur in succession
 - 3. each individual aura symptom lasts 5–60 minutes
 - 4. at least one aura symptom is unilateral
 - 5. at least one aura symptom is positive
 - 6. the aura is accompanied, or followed within 60 minutes, by headache
- D. Not better accounted for by another ICHD-3 diagnosis.

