### Diagnostic criteria:

- A. At least two attacks fulfilling criteria B and C
- B. One or more of the following fully reversible aura symptoms:
  - 1. visual
  - 2. sensory
  - 3. speech and/or language
  - 4. motor
  - 5. brainstem
  - 6. retinal
- C. At least three of the following six characteristics:
  - 1. at least one aura symptom spreads gradually over  $\geq 5$  minutes
  - 2. two or more aura symptoms occur in succession
  - 3. each individual aura symptom lasts 5–60 minutes
  - 4. at least one aura symptom is unilateral
  - 5. at least one aura symptom is positive
  - 6. the aura is accompanied, or followed within 60 minutes, by headache
- D. Not better accounted for by another ICHD-3 diagnosis.

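### The SAP's migraine-day count has no aura route, although the protocol enrols on ICHD-III migraine days in patients with or without aura; the size and direction of the effect are unknown

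*SAP*

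**What the plan says.** **Entry.** Protocol 4.1 describes the population as participants "with at least 4 and up to 20 migraine days per month (inclusive) following ICHD-III criteria for migraine with or without aura". To enrol at Visit 2 they must have "experienced 4-20 migraine days that meet ICHD-III criteria for migraine" during the run-in. Inclusion 5 (Protocol 5.1) asks that they "have migraine with or without aura meeting the diagnostic criteria listed in the International Classification of Headache Disorders 3rd edition". Inclusion 6 repeats the 4-20 range and does not mention aura. SAP 1.2 carries over the Protocol 4.1 text.

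**Printed criteria.** Both documents reproduce the ICHD-3 criteria for migraine with aura (Protocol 10.5, SAP Appendix 6.2.2). Criterion B is "One or more of the following fully reversible aura symptoms". Criterion C is three of six characteristics, of which headache is one: "the aura is accompanied, or followed within 60 minutes, by headache". The aura criteria set no pain quality, no four-hour duration and no associated symptom.

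**Endpoint.** SAP 4.3.4.1 states: "Migraine headache days are defined in this study as an attack within a calendar day (00:00 to 23:59) that meet at least one" of two criteria. The first is a 4-72 hour headache for which "Headache has at least two of the following four characteristics", with nausea or vomiting, or photophobia and phonophobia. The second is a headache of any duration relieved by a listed acute treatment. SAP 4.3.4.2 uses this count for baseline and for treatment months 1 to 3. SAP 4.8 declares no change to the protocol-planned analyses, and neither document explains why aura is left out.

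**The concern.** The first SAP route is the without-aura definition (criteria B to D). The second depends on treatment and relief. A participant who is eligible because of migraine with aura can therefore have days that the protocol's own criteria call migraine and that the endpoint never sees. Number of migraine days is a named secondary endpoint, and its baseline is taken from the same run-in that decides entry. If entry and analysis count different days, the report could describe a population with 4-20 migraine days while some analysed baselines lie below 4, or above 20, with nothing in the plan to reveal it.

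**Working it through.** **The plan's own figure.** The only derived figure is N = 54 for the primary paired t-test. With d = 0.50, two-sided alpha 0.05 and n = 54, the noncentrality is 0.50 × √54 = 3.674 on 53 degrees of freedom. Power is 0.9502, and 54 is the smallest n that reaches 0.95. The figure reproduces, and it does not use migraine days.

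**Which days are lost.** Compare the printed aura criteria with the two SAP routes:

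| Day meeting aura criteria B and C | Route 1 | Route 2 | Counted |
|---|---|---|---|
| Aura, headache with full without-aura features | yes | not needed | yes |
| Aura, short or mild headache, relieved by a listed product | no | yes | yes |
| Aura, short or mild headache without the full features, untreated or not relieved | no | no | no |
| Aura, no headache | no | no | no |

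The last row is possible under the printed text. Three or more of six characteristics can be met in 20 + 15 + 6 + 1 = 42 ways. Of these, 10 + 5 + 1 = 16 leave out the headache item. These are logical combinations and say nothing about frequency.

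**Which days may be gained.** Route 2 takes any relieved headache, however short. The printed without-aura duration of 4-72 hours is for attacks that are untreated or unsuccessfully treated. The entry text has no relief rule, so a short relieved headache counts in the analysis but may not have counted at entry.

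**Size of the loss, on assumptions.** The documents give neither the share of participants with aura nor the share of their days that qualify only through it. Assume 10-40% and 10-50%, with equal day counts per participant:
- low: 0.10 × 0.10 = 1% of all migraine days
- high: 0.40 × 0.50 = 20%
- at an assumed mean of 10 days a month: 0.1 to 2.0 days off the average baseline

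This is a gross loss. Days gained through route 2 work against it and cannot be sized either.

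**Effect on the change score.** Let B and F be the ICHD-III days at baseline and follow-up, and q0 and q1 the aura-only shares. With no route 2 gains, the counted change is F(1 − q1) − B(1 − q0). Take B = 8 and F = 5 for illustration, a true change of −3.0:

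| q0 | q1 | Counted baseline | Counted follow-up | Counted change |
|---|---|---|---|---|
| 10% | 10% | 7.2 | 4.5 | −2.7 |
| 20% | 20% | 6.4 | 4.0 | −2.4 |
| 10% | 30% | 7.2 | 3.5 | −3.7 |
| 30% | 10% | 5.6 | 4.5 | −1.1 |

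The change shrinks in proportion only when the share is the same in both periods.

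**Entry floor.** A participant enrolled on exactly 4 days has an expected counted baseline of 4 × 0.9 = 3.6 at a 10% share and 4 × 0.8 = 3.2 at 20%, before any route 2 gain.

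**The case against.** The strongest reply is that no second counting rule exists. The protocol gives diagnostic criteria for a disorder, which are not an algorithm for classing a diary day. Its Visit 2 rule says only ICHD-III criteria for migraine; the aura wording is in the population sentence and in inclusion 5. The SAP rule is the only day-level rule in either document, and it is applied to the run-in. If sites used it at entry, the two counts agree. That stands, and it rules out a claim that the counts did diverge. It does not remove the point. The population sentence ties the 4-20 days to both forms of migraine, and the protocol gives sites no such rule. SAP version 1 is dated 13 October 2021 against a protocol of 16 September 2020. Even a shared rule would leave aura-only days out of an endpoint for patients admitted with aura.

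A reader might infer that someone could enter with six aura days and be analysed with a baseline of zero. The wording allows this, but only if sites counted aura days at entry and every one of the six missed both routes. The documents do not show that it happens. Route 2 is broad, covering common analgesics as well as triptans, and may recover many aura days.

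A reader might also infer that the result is biased toward zero. One rule applies in every period, and the table above shows error in both directions.

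The SAP does prevail over the protocol in a discrepancy (Protocol 9.4). That settles which analysis is run. It does not make the analysed baseline match the population described.

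**Conclusion.** The mismatch is in the text: as written, SAP 4.3.4.1 does not count days that qualify only through the printed aura criteria, at baseline or on treatment. The entry count and the analysed baseline may differ in either direction, because the entry rule is not specified at day level. The 1-20% gross loss rests wholly on the assumed shares, and the true figure may be small. The sign of any effect on the change score is unknown. Proportional shrinkage needs a constant aura-only share and no offsetting route 2 gains. The point is confined to one secondary endpoint; MFIQ item 16 and the sample size are unaffected. It merits a correction because the rule departs from the protocol's own criteria and the remedy is cheap.

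**What to change.** Add a third route to SAP 4.3.4.1: a headache day with aura meeting criteria B and C of Appendix 6.2.2. State explicitly whether an aura day without headache counts, since the printed criteria allow one and both present routes require a headache. Apply the same programmed count to the run-in days used for inclusion 6, to the analysed baseline and to each treatment month.

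Protocol 8.1.3 and SAP 4.3.4.2 say that the diary records symptoms, but they do not say whether aura is among them. If it was not captured, recompute the run-in count under the existing SAP rule, report how many enrolled participants fall outside 4-20, and state that the endpoint excludes aura-only days.

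The cost is SAP wording and some programming. The fallback needs only existing diary entries and a sentence in the report. The downsides are counts that differ slightly from those under a without-aura definition, and dependence on aura having been recorded.
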